4.3. Clinical investigation risks and benefits

4.3.1. Anticipated benefits to participants

The clinical studies conducted in adults demonstrated that REN provides superior clinically meaningful relief of migraine pain and MBS compared to sham-device with a favorable safety profile, offering a safe and effective non-pharmacological alternative for acute migraine treatment. It is anticipated that adolescents with migraine will experience a similar clinically beneficial effect.

4.3.2. Risks and adverse effects

The results of the pivotal study demonstrate a favorable safety profile of the device. In this study, adverse event incidence was low; mainly reports of sensation of warmth, redness and numbness of the arm/hand. All device-related adverse events were mild, resolved within 24 hours and did not require medical treatment. There were no device-related serious adverse events, no unanticipated adverse device effects and none of the participants withdrew from the study due to adverse events. The safety profile of the device is favorable compared to triptans [27] and to new pharmacological agents, such as centrally acting serotonin (5-HT1F) agonists that lack cardiac vasoconstrictive activity [28]. Furthermore, the device has comparable or superior efficacy to commercially available neuromodulation devices [23,26].

4.3.3. Risk-benefit balance

The data collected in the randomized controlled clinical study in adults demonstrated that acute treatment of migraine with Nerivio™ results in most important clinical benefits with a very low risk to the patient. Invoking conditioned pain modulation using peripheral neurostimulation that induces a general analgesic effect resulted in favorable 2-hour pain relief and pain-free responses which are comparable with pharmacological acute migraine treatments such as triptans with a more favorable safety profile. Overall, the benefit-risk balance of Nerivio™ is favorable. The overall risk posed by the device is minimal. The device offers a major benefit by providing a novel acute treatment of migraines which is highly effective and reduces the side effects of current pharmacological treatments. Therefore, the device may offer an alternative non-pharmacological treatment approach to the limited effective treatment options in adolescents and has the potential to decrease the reliance of patients on pharmacological treatments, improve treatment adherence, reduce the risk of medication overuse and considerably improve the health and quality of life of adolescents with migraine.

Nerivio TCH-004 Clinical Study Protocol (NCT04089761)

Doc ID: TEC0105

Revision #: 1.0 Page: 26 of 49

5. Objectives & hypotheses

5.1. Study objectives

The objective of this study is to evaluate the safety and efficacy of Nerivio[™] for the acute treatment of migraine with or without aura in adolescents. The goal of this study is to demonstrate migraine headache relief without unexpected device-related adverse effects.

5.2. Study hypothesis

The hypothesis of this study is that in adolescents, REN with Nerivio[™] will provide clinically meaningful relief of migraine pain with a favorable safety profile.

6. Study design

6.1. Participants

This study will be conducted on up to 130 eligible participants.

6.1.1. Inclusion criteria

- Participants age 12-17 years old at the time of informed consent, inclusive.
- Participants have at least a 6-month history of headaches that meet the ICHD-3 diagnostic criteria for migraine with or without aura
- History of at least 3 migraine attacks per month for each of the 2 months preceding study enrolment
- Typical headache duration of at least 3 hours (when untreated or unsuccessfully treatment)
- Stable migraine preventive medications during the 2 months prior to enrollment (no change in usage or dosage).
- Participants have personal access to a smartphone (24/7)
- Participants must be able and willing to comply with the protocol
- Parents/Guardians must be able and willing to provide written informed consent
- Participants must be able and willing to provide informed assent

6.1.2. Exclusion criteria

- Participants with an implanted electrical and/or neurostimulator device (e.g. cardiac pacemaker, cochlear implant).
- Subjects with congestive heart failure (CHF), severe cardiac or cerebrovascular disease.
- · Participants with epilepsy.
- Medical use of cannabis or recreational use one month prior to enrollment

theranica CONNECTED HEALTHCARE

QMS document

Nerivio TCH-004 Clinical Study Protocol (NCT04089761)

Doc ID: TEC0105

Revision #: 1.0

Page: 27 of 49

- Participants who have undergone nerve block (occipital or other) in the head or neck within the last 2 weeks
- Treatment with onabotulinum toxin A (Botox) to the head and/or neck for 3 months before enrollment and/or during the study
- Any history of anti-CGRP antibody treatment
- Current participation in any other clinical study that includes treatment
- Participants without basic cognitive and motor skills required for operating a smartphone.
- Pregnant or breastfeeding females
- Pure menstrual migraine
- Participants who received parenteral treatments for migraine within the previous 2 weeks.
- Participants with other significant pain, medical or psychological problems that in the opinion of the investigator may confound the study assessments
- Participants who have previous experience with the device
- Participants with upper arm circumference below 7.9 inches (20 cm)

6.1.3. Contraindications

- The device should not be used by people with congestive heart failure (CHF), severe cardiac or cerebrovascular disease.
- The device should not be used by people with uncontrolled epilepsy.
- The device should not be used by people with active implantable medical device, such as a pacemaker, hearing aid implant, or any implanted electronic device. Such use could cause electric shock, electrical interference or serious injuries or medical conditions.

Main warnings and precautions:

- The device should not be used over skin conditions, such as open wounds or rashes, or over swollen, red, infected or inflamed areas or skin eruptions or fragile skin on the upper arm at the treatment location.
- The device should not be shared with other people. The device is intended to be used by a single person to avoid skin disease or any transmissible disease.
- The device should not be used on the heart, chest, neck, head or any other body location other than the upper arm, because this could cause severe muscle spasms resulting in closure of your airway, difficulty in breathing, or adverse effects on heart rhythm or blood pressure.
- The device has not been evaluated for use in pregnant women

Nerivio TCH-004 Clinical Study Protocol (NCT04089761)

Doc ID: TEC0105

Revision #: 1.0 Page: 28 of 49

6.1.4. Withdrawal/discontinuation

Participants may withdraw consent at any time without and do not have to provide an explanation.

Participant may be withdrawn from the study by the PI or sponsor due to one or more of the following reasons:

- Participant is lost to follow-up
- Refusal of the participant to continue treatment and/or follow-up observations
- Serious adverse event
- Participants encountering difficulties with the investigational product (IP) (e.g. cannot tolerate the treatment, unable to operate the application)
- Significant protocol deviation/violation or noncompliance, either by the patient or the investigator
- Decision made by the investigator that termination is in the patient's best medical interest
- Device malfunction
- Other ethical or clinical considerations upon investigator discretion

6.2. Stimulation program

The device produces a proprietary electrical signal comprising a modulated symmetrical biphasic square pulse with a modulated frequency of 100-120-Hz, pulse width of 400 μ s, and up to 40 mA output current (adjusted by the participant). The duration of the treatment is 45 minutes.

6.3. Procedures

This open label study includes 3 phases and up to 4 visits. All visits will be conducted in the presence of a parent/guardian.

First visit – enrollment: The first visit will include screening, enrollment and training on the application in diary mode. The screening process will include an eligibility assessment and a urine pregnancy test. Following successful screening, enrollment interview and signing an informed consent by the parent/guardian and an informed assent by the participant. The participants will be trained to use the electronic diary application, installed on their own smartphones. The site personnel will be required to document the training session in the CRF. During this visit, participants will complete baseline questionnaires that included information on the frequency and severity of their migraine attacks, typical associated symptoms, use of preventive and acute treatments, and the effect that their migraine attacks have on their daily routine and quality of life.

Nerivio TCH-004 Clinical Study Protocol (NCT04089761)

Doc ID: TEC0105

Revision #: 1.0

Page: 29 of 49

Phase 1 – run-in phase: After the enrollment visit, participants will undergo a 4-week migraine diary phase aimed to collect baseline migraine characteristics and further assess eligibility. Participants will be asked to report in the application each migraine attack. These reports will be transferred by the application to the electronic data collection (EDC) system, where they will be collected and registered. Participants who did not have at least 3 migraine attacks will be excluded from the study. Eligibility will also be determined based on the compliance of participants to report the attacks within one hour from attack onset and report the pain level at 2 hours post-treatment in at least 66.7% of the reported attacks.

Second visit – **Device training visit:** Eligible participants who meet the run-in requirements will receive the Nerivio[™] device. The device will be registered and connected by Bluetooth to their smartphone. During this visit, participants and their parent/guardian will be trained to use the device, including finding the optimal individual stimulation intensity level (perceptible but not painful). The site will also carefully review with the patient and parent/caregiver how to identify a qualifying migraine attack (see below) and provide detailed instructions on study procedures.

The individual intensity level identified during this visit will be recorded, and the participants will be asked to treat their migraine headaches with the device using the identified intensity. If the research staff recognizes that the participant cannot tolerate the feeling of the electrical stimulation, the participant may be withdrawn from the study.

During the training, participants will also be informed on the key elements which are critical for the successful conduct of the study:

- Treatments of attacks with Nerivio[™] should be performed as soon as possible
 after migraine headache or aura began and always within one hour of symptoms
 onset. Treatments of mild headaches are accepted.
- Avoid taking rescue medications within two hours post-treatment (2 hours from start of treatment), if possible.
- The treatment should be performed for at least 30 minutes (the recommended treatment duration is 45 minutes).

Phase 2 –Treatment phase: Participants will be instructed to use the device for the treatment of 4 qualifying migraine attacks (see below) as soon as possible and always within 60 minutes of onset during a period of up to 8 weeks. Participants will be instructed to use the device with the intensity level identified during the device training visit (with a range of ±5 units) and make sure the stimulation is perceptible but not painful. Participants will be instructed to avoid taking rescue medications within 2 hours post-treatment. If medications are used, participants will be instructed to record in the app when and which medication was taken. The participants will use the app to record pain intensity levels (none, mild, moderate, or severe) at baseline, 2- and 24-hours post-treatment, and to record the presence/absence of associated migraine symptoms (nausea, photophobia,

Nerivio TCH-004 Clinical Study Protocol (NCT04089761)

Doc ID: TEC0105

Revision #: 1.0

Page: 30 of 49

phonophobia) at baseline and 2 hours post-treatment. To assess functional disability, participants will also record at baseline, 2- and 24-hours post-treatment their response to the following question in their diary: "How do you rate your ability to do school-work or perform your usual activities?" using a 4-point scale ('as usual', 'some ability', 'a little ability', 'no ability at all'). At the beginning of each treatment, participants will also be asked to report the time elapsed from attack onset. Adverse events will be reported throughout this phase of the study.

Participants who do not achieve satisfactory relief at 2 hours post-treatment may treat again with the Nerivio[™] device or may treat with usual care at that time or any time thereafter if the headache does not resolve. Participants will also be able to treat headache recurrence with the device. Attacks that are not treated with the device may be treated with usual care.

The first reported treatment will be considered a "training" treatment, aimed to verify that the participants use the device properly, and will only be included in the safety analysis. The efficacy evaluation will be performed on the first treatment of a qualifying attack (see below) following the training treatment (hereby termed "test treatment").

Qualifying migraine attack

A qualifying migraine attack is defined as a migraine attack that:

- 1. Was not preceded by another migraine or other headache within the preceding 24 hours
- 2. Was not preceded by the use of specific or non-specific acute migraine medications within the previous 24 hours
- Occurred in a setting in which the patient could properly administer the treatment (that is, it is possible to initiate a complete treatment within 60 minutes of onset and the participant will be able to complete the migraine diary at 2 hours after treatment)

Third visit – Termination of the treatment phase and free-use phase initiation: Following the 8-week period of the treatment phase, participants will return to the clinic to return the device and fill questionnaires assessing satisfaction and user experience. All participants who complete the treatment phase will be offered to participate in an additional 8-week phase in which the device can be incorporate into usual care.

Phase 3 – Free-use phase: Participants will continue in an 8-week phase in which they will be able to use the device according to their preferences for the treatment of their migraine attacks.

Fourth (final) visit – End of study: Participants will return to the clinic following the end of the 8-week free-use phase, at which time they will return the device.

Nerivio TCH-004 Clinical Study Protocol (NCT04089761)

Doc ID: TEC0105

Revision #: 1.0 Page: 31 of 49

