Informed consent and assent must be obtained from the parent/caregiver and participant, respectively, before any protocol-related activities are performed. Participants must be provided with a signed copy of the consent and assent forms. The eCRFs will be updated that informed consent and assent have been signed.

12. Adverse events

Adverse event (AE) is defined as any unfavorable and unintended medical change, temporally associated with the use of the sponsor's product, whether or not considered related to the use of the product. Any worsening (i.e., any clinically significant adverse

Nerivio TCH-004 Clinical Study Protocol (NCT04089761)

Doc ID: TEC0105

Revision #: 1.0

Page: 43 of 49

change in frequency and/or intensity) of a preexisting condition which is temporally associated with the use of the sponsor's product, is also an adverse experience. An adverse device effect (ADE) is an adverse event related to the use of the investigational device. In this study the ADE refers to side effect and complications.

A serious adverse event (SAE) is defined as an adverse event that leads to a) death,

- b) serious deterioration in the health of the subject, that either resulted in
 - 1) a life-threatening illness or injury, or
 - 2) a permanent impairment of a body structure or a body function, or
 - 3) in-patient or prolonged hospitalization, or
 - 4) medical or surgical intervention to prevent life-threatening illness or injury or permanent impairment to body structure or body function
- c) fetal distress, fetal death or a congenital abnormality or birth defect

A serious device related adverse effect (SADE) is an adverse event related to the use of the investigational device and that is considered by regulations and definitions as serious.

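### The only specified pregnancy test comes about 4 weeks before the first stimulation, and nothing re-checks pregnancy at the visit where stimulation starts

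*Combined protocol and SAP*

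**What the plan says.** Pregnancy is an entry exclusion in section 6.1.2 ("Pregnant or breastfeeding females"). Among the warnings and precautions in section 6.1.3 the protocol adds: "The device has not been evaluated for use in pregnant women".

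Section 6.3 sets out the visits:

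- **Visit 1 (enrollment).** "The screening process will include an eligibility assessment and a urine pregnancy test". This is the only pregnancy test named anywhere in the text.
- **Run-in.** After visit 1, "participants will undergo a 4-week migraine diary phase aimed to collect baseline migraine characteristics and further assess eligibility". The device is not in use. The stated conditions for continuing are at least 3 attacks (the synopsis adds a duration requirement) and timely diary reporting.
- **Visit 2 (device training).** "Eligible participants who meet the run-in requirements will receive the Nerivio" device. At the same visit "participants and their parent/guardian will be trained to use the device, including finding the optimal individual stimulation intensity level". Staff also judge whether the participant tolerates the sensation, so current is delivered here.
- **Visits 3 and 4.** Visit 3 has device return and questionnaires, followed by optional free use; visit 4 has device return. No pregnancy test is listed at either.

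A pregnancy that is already known can be acted on under the general grounds in section 6.1.4, for example "Other ethical or clinical considerations upon investigator discretion". The serious adverse event definition in section 12 includes "fetal distress, fetal death or a congenital abnormality or birth defect".

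**The concern.** The test sits at the entrance to a phase with no device exposure, and its result is about 4 weeks old when exposure begins. Two kinds of pregnancy pass through every specified check: one too early to show at visit 1, and one that starts during the run-in. The run-in is described as a further eligibility step, but the exclusion that bears on exposing a fetus is not part of it.

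What is at stake is participant safety and adherence to the protocol's own exclusion in 12- to 17-year-olds. No bias in the primary safety and tolerability endpoints, the efficacy proportions or the sample size is alleged.

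**Working it through.** **Inputs**

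- Test at visit 1, week 0 (section 6.3).
- Run-in of 4 weeks, then visit 2 with first stimulation (section 6.3).
- Treatment phase of up to 8 weeks, then optional free use of 8 weeks (section 6.3).
- Up to 130 participants (section 6.1); 110 before the allowance for drop-out (section 7.3).

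**Reproducing the plan's own duration.** Run-in plus treatment is 4 + 8 = 12 weeks, and free use adds 8, giving 20. This agrees with section 6.3.1 (about 12 weeks, plus 8).

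**Age of the latest test result** (time point minus time of last test)

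| Time point | Week | As planned (test at week 0) | With a test at visit 2 (week 4) |
|---|---|---|---|
| First stimulation | 4 | 4 − 0 = 4 | 4 − 4 = 0 |
| End of treatment phase | 12 | 12 − 0 = 12 | 12 − 4 = 8 |
| End of free use | 20 | 20 − 0 = 20 | 20 − 4 = 16 |

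**What each test can catch before exposure.** No stimulation takes place before visit 2. A pregnancy detectable at visit 1 that continues is still detectable at visit 2. A visit 2 test therefore finds every continuing pregnancy that the visit 1 test would find, plus those that arise or become detectable in the 4 weeks between. It misses only a pregnancy not yet detectable at visit 2, which the visit 1 test would miss as well.

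**Scale.** The expected number of cases before first exposure is F × q, where F is the number of female participants who reach visit 2 and q is the probability per participant of a pregnancy arising or becoming detectable in the run-in. The documents give neither. The q needed for one expected case is 1/F:

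- F = 130 (every participant female): 1/130 = 0.77%.
- F = 110: 1/110 = 0.91%.
- F = 0.809 × 130 ≈ 105, assuming the female share in the adult pivotal study (section 4.2.2, Table 4) carried over: 1/105 ≈ 0.95%.

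These are break-even values. They say nothing about how often a case would occur.

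**The case against.** The strongest reply is that testing at screening for an entry criterion is a coherent choice. The botulinum toxin criterion in the same list is worded to run on into the study, while the pregnancy criterion is not. Pregnancy is not among the contraindications in section 6.1.3; it appears only as a precaution. The documents identify no fetal hazard and describe the overall risk as minimal. The longer unprotected period is the up to 16 weeks of device access after visit 2, which a visit 2 test leaves alone, and nothing in the documents makes the first stimulation riskier than later ones. Known pregnancies can be handled under section 6.1.4, and fetal harm is reportable. Finally, a parent or guardian attends every visit, so a repeat test creates a second sensitive disclosure situation for a minor.

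Much of this stands and limits the weight of the point. No hazard has been shown, no frequency can be given, and the fix is partial. None of it supplies a check before first exposure, however. Investigator discretion works only on a pregnancy that is known, and section 6.3 requires nobody to ask or test at visit 2. Serious adverse event reporting acts after exposure. The uncovered later weeks do not justify leaving uncovered the one point where a planned visit and the start of exposure coincide. The disclosure issue applies equally to the visit 1 test, and moving that test adds no second occasion.

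**Conclusion.** The concern holds. As written, the plan's only objective check on pregnancy is about 4 weeks old at first stimulation, and a pregnancy that arises or becomes detectable during the run-in is not caught by any specified procedure. A test at visit 2 reduces that interval to 0. The later ages fall only from 12 to 8 weeks and from 20 to 16.

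This is a low-cost safety improvement to consider. It has no consequence for the statistical analysis, and the number of participants affected cannot be estimated from the documents.

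The conclusion assumes that section 6.3 is the operative visit schedule. The available text contains no schedule-of-assessments table. The instructions for use, case report forms and monitoring plan are separate documents, and the consent pages were not available, so any instruction there to ask about or report pregnancy could not be seen.

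**What to change.** In section 6.3, under the second visit, specify a urine pregnancy test for female participants, with the result known before the device is applied for intensity finding. There are two ways to do it:

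- **Repeat:** keep the visit 1 test and add one at visit 2. The cost is one extra urine test per female participant reaching a visit that is already planned. The enrollment check is retained.
- **Move:** shift the existing test from visit 1 to visit 2. This adds no procedure. The drawback is that the exclusion goes untested at enrollment, so a pregnant participant may complete the 4-week diary before being excluded.

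Either secures first exposure, apart from a pregnancy still undetectable at visit 2. Neither covers the 8 to 16 weeks of device access that follow. The sample size, endpoints and analyses stay as they are.

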6.4.2. Secondary endpoints

1. Pain relief at 2 hours post-treatment:

The proportion of participants achieving pain relief, defined as improvement from severe or moderate pain to mild or none, or improvement from mild pain to none, at 2 hours post-treatment in the test treatment, with no use of rescue medication

- 2. Pain-free at 2 hours post-treatment:
 - The proportion of participants achieving pain freedom, defined as improvement from mild, moderate, or severe pain to none, at 2 hours post-treatment in the test treatment, with no use of rescue medication
- 3. Disappearance of associated symptoms at 2 hours post-treatment
 - a. The proportion of participants reporting nausea at baseline and achieving absence of nausea at 2 hours post-treatment in the test treatment
 - b. The proportion of participants reporting phonophobia at baseline and achieving absence of phonophobia at 2 hours post-treatment in the test treatment
 - c. The proportion of participants reporting photophobia at baseline and achieving absence of photophobia at 2 hours post-treatment in the test treatment

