7.2.2. Secondary endpoints

Secondary efficacy endpoints include:

- Proportion of subjects reporting, for the test treatment, pain relief at 2 hours post treatment without use of rescue medication. Pain relief is defined as an improvement from severe or moderate pain to mild or no pain, or from mild pain to no pain.
- Proportion of subjects reporting, for the test treatment, pain-free at 2 hours post treatment without use of rescue medication. Pain free is defined as an improvement from mild, moderate or severe pain to no pain.
- Proportion of subjects reporting, for the test treatment, nausea at baseline and achieving absence of nausea at 2 hours post treatment without use of rescue medication.
- Proportion of subjects reporting, for the test treatment, phonophobia at baseline and achieving absence of phonophobia at 2 hours post treatment without use of rescue medication.
- Proportion of subjects reporting, for the test treatment, photophobia at baseline and achieving absence of photophobia at 2 hours post treatment without use of rescue medication.

Nerivio TCH-004 Clinical Study Protocol (NCT04089761)

Doc ID: TEC0105

Revision #: 1.0 Page: 35 of 49

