7.5. Statistical analysis

7.5.1. General considerations

Statistical analyses will be performed using SAS® v9.4 or higher (SAS Institute, Cary NC, USA).

Baseline demographic and other baseline characteristics, together with safety analyses will be performed on all participants who underwent the treatment phase. Baseline values are defined as the last valid value prior to treatment.

Where confidence limits are appropriate, a two-sided 95% confidence interval will be constructed.

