7.5.4. Efficacy analysis

The efficacy endpoints will be assessed on evaluable treatments of qualifying attacks. The first use of the device is considered a training treatment and will not be included in the efficacy analyses. The first treatment of a qualifying attack after the training treatment is considered a test treatment and will be used for all efficacy assessments. If this treatment is not evaluable (i.e., no pain data at 2 hours post-treatment), a subsequent treatment of a qualifying attack with evaluable data will be considered the test treatment.

Use of rescue medication before the 2-hours assessment will be considered a treatment failure for the 2-hours endpoints, and before the 24 hours assessment for the sustained

Nerivio TCH-004 Clinical Study Protocol (NCT04089761)

Doc ID: TEC0105

Revision #: 1.0

Page: 37 of 49

24-hours endpoints. The percentage of participants achieving each of the efficacy outcomes will be presented in a tabular form along with two-sided 95% exact confidence intervals.

For the associated symptoms outcomes, the observed response proportions and corresponding 95% exact confidence intervals for each associated symptom will be provided. All patients with baseline and 2 hours values will be included in the analyses. A response in each associated symptom (nausea, vomiting, photophobia, phonophobia) is defined as change from presence of a specific associated symptom at baseline to absence of the same associated symptom at 2 hours post-treatment.

In addition, logistic regression models will be used to assess the efficacy. Baseline value and site will serve as covariates.

The first secondary endpoint (pain relief at 2 hours) may also be evaluated in attacks with aura and attacks without aura separately.

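### A test treatment started in aura with no pain stays in the denominator of both 2-hour pain endpoints but, read literally, can never be a response

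*Combined protocol and SAP*

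**What the plan says.** The device-training instructions in section 6.3 allow treatment to begin once either headache or aura is present: "after migraine headache or aura began and always within one hour of symptoms" is the operative wording. The next sentence adds "Treatments of mild headaches are accepted". In the treatment phase, participants "record pain intensity levels (none, mild, moderate, or severe) at baseline" and again later, so *none* is an available baseline answer. Section 7.5.1 fixes which value counts: "Baseline values are defined as the last valid value prior to treatment". Migraine with aura is eligible (6.1.1), and the existing adult indication in 3.1 also names aura as a starting point.

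The endpoint definitions start one grade higher. In 6.4.2, pain relief is "defined as improvement from severe or moderate pain to mild or none, or improvement from mild pain to none, at 2 hours post-treatment", and pain freedom is "defined as improvement from mild, moderate, or severe pain to none, at 2 hours post-treatment in the test treatment". Section 7.2.2 repeats the latter: "Pain free is defined as an improvement from mild, moderate or severe pain to no pain".

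The qualifying-attack definition in 6.3 has three conditions: no headache in the prior 24 hours, no acute medication in the prior 24 hours, and a suitable setting. None concerns pain at the start of treatment. The mITT set in 7.4 needs a test treatment within 60 minutes of onset and a valid post-baseline value. The per-protocol list adds no baseline-pain condition. Section 7.5.4 replaces a test treatment on one ground only, beginning "If this treatment is not evaluable (i.e., no pain data at 2 hours post-treatment", and then moves to a later qualifying treatment that has the data.

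**The concern.** A participant who treats during aura, records no pain, and still has none at 2 hours has had the best possible pain outcome. Under the definitions as written, that participant sits in the denominator of both pain endpoints and cannot enter either numerator. The reported rate would then mix two different things: pain that did not respond, and no pain to relieve.

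This touches the endpoint on which section 7.3 bases the sample size. The sustained 24-hour endpoints in 7.2.3 require the 2-hour response first, so they inherit the problem. The logistic model in 7.5.4 takes the baseline value as a covariate. If baseline pain enters as categories, the *none* level has no responders by construction and its coefficient cannot be estimated in the usual way. The study is single-arm, so no concurrent control would shift in parallel. If the rule stays open, the analyst must decide on these cases after the outcomes are known.

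**Working it through.** **1. Each rule applied to one case: a qualifying attack, treated in aura within the hour, pain *none* at baseline and *none* at 2 hours.**
- Qualifying attack (6.3): all three conditions can be met.
- mITT (7.4): treated in time, with a post-baseline value, so included.
- Per-protocol (7.4): on time, qualifying, at least 30 minutes, 2-hour pain recorded, no rescue medication. Included.
- Evaluable (7.5.4): 2-hour pain is present, so not replaced.
- Missing data (7.5.6): nothing is missing, so not triggered.
- Pain relief and pain freedom (6.4.2, 7.2.2): both need baseline mild or worse, so neither can be met.

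Result: in the denominator, never in the numerator.

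**2. The plan's own figure.** Section 7.3 gives 110 participants, 60% (±6%) and 80% power. As a precision calculation, n = z² × p × (1 − p) / d², with p = 0.60 and d = 0.06. Using z = 1.2816 (80% confidence), n = 1.2816² × 0.24 / 0.0036 = 109.5, so 110. With 15% drop-out, 110 / 0.85 = 129.4, so 130. Both figures reproduce, with the 80% acting as a confidence level. The 95% half-width at n = 110 is 1.96 × √(0.24 / 110) = 9.2 points.

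**3. Size of the shift.** Let f be the share of test treatments with baseline *none*. The documents give no value for f; the range here is assumed. With 60% relief among attacks that have pain, the expected rate is 0.60 × (1 − f):
- f = 5%: 0.60 × 0.95 = 57%
- f = 10%: 0.60 × 0.90 = 54%
- f = 20%: 0.60 × 0.80 = 48%

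Worked example at n = 110 and f = 10%: 11 start without pain and 99 with pain; 0.60 × 99 = 59.4, taken as 59 responders. Keeping all participants gives 59/110 = 53.6% (exact 95% CI 43.9 to 63.2). Restricting to those with baseline pain gives 59/99 = 59.6% (49.3 to 69.3).

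**4. What the adult study shows (4.2.2, Table 4).** Baseline pain in the test treatment was mild, moderate or severe in 35 + 57 + 7 = 99 of 99 active and 43 + 46 + 14 = 103 of 103 sham participants. Aura was present in 19/99 and 20/103. So no adult test treatment in the mITT set began without pain, despite aura in about 19%. The adult timing instruction, however, referred to the start of headache and did not name aura.

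**The case against.** The strongest reply is that the plan nowhere says a no-pain start is a failure. Defining response as improvement from mild or worse could be read as limiting the pain endpoints to attacks with pain, and section 6.3 speaks of treating migraine headaches and names mild as acceptable. It is right that the scoring is inferred. But accepting mild headaches excludes nothing, and 7.5.4 spells out what makes a treatment non-evaluable: absent 2-hour pain data. No denominator is restricted by baseline pain. Section 9.1 mentions a separately held statistical analysis plan that may settle this; the text available here does not.

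A second reply concerns size. A reader might take the adult aura figure of 19.2% as the no-pain share, giving 0.60 × 0.808 = 48.5%, or suppose that half of aura attacks start without pain and read 60% as 30% in that subgroup. The documents support neither. Every adult attack with aura had pain at baseline, and no source gives a one-half share. The adult zero cannot simply be carried over, because the instruction differed, but it is the only evidence on the point.

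A reader might also infer that a shift of 6 points would overturn the trial's conclusion. It would not. The primary endpoints are safety and tolerability, the pain endpoints are secondary with no success threshold, and in the f = 10% example the 95% interval still covers 60%. The separate look at attacks with and without aura is optional, and section 7 plans no comparison with the adult result. All of this limits the consequence; it does not close the gap.

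**Conclusion.** The point stands as a mismatch between the treatment-start rule and the endpoint definitions, with no rule to bridge it. On a literal reading, the pain-relief rate is lowered by 0.60 × f: 3 points at f = 5% and 6 points at f = 10%. This assumes 60% relief among attacks with pain and that every no-pain start remains in the denominator. Because f is unknown and was zero in the adult study, the effect may be small. It biases against the device, so it cannot create a false impression of efficacy. It is still worth correcting before database lock, because the handling should be settled before results are seen and the remedy is cheap.

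**What to change.** Leave the instruction on when to treat as it is. In 6.3, 7.4 and 7.5.4, and in the synopsis, extend the evaluability rule: the test treatment is the first qualifying attack after the training treatment that has at least mild pain recorded at the start of treatment and pain data at 2 hours; otherwise the next such attack in order. Use that same treatment for all efficacy endpoints. Section 7.5.4 assigns one test treatment to every efficacy assessment, and a rule for the pain endpoints alone would let one participant's outcomes come from different attacks.

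Report treatments begun without pain on their own line: how many, and how many were still pain-free at 2 hours. Add a sensitivity analysis that keeps the first post-training qualifying treatment with 2-hour data, as 7.5.4 now selects it, and counts no-pain starts as failures, so that any gain from the restriction is visible.

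The cost is a sentence in each of these places, one table line and one extra analysis. The baseline pain data are already collected, and the added criterion uses only a pre-treatment value. Participants are asked to treat four attacks, so many should have a replacement. The downside is that a few whose only post-training treatments began without pain will leave the main efficacy denominator.
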